13.2.2.2 Over the Counter Analgesic Usage

The change in daily average use of over the counter analgesics comparing the baseline menstrual cycle to a similar period leading up to the last day of dosing in Cycle 1 (Week 18) will be summarized for each treatment group. For each subject, the total number of doses of over the counter analgesics during each menstrual cycle will be calculated, and the daily average use of over the counter analgesics will be determined by dividing the total number of doses of over the counter analgesics by the number of days in the menstrual cycle

(number of doses per day). The percent change from baseline in the over the counter analgesic usage will be determined by subtracting the baseline over the counter analgesic usage from the over the counter analgesic usage during each menstrual cycle, dividing by the baseline over the counter analgesic usage, and multiplying by 100%.

An overall comparison among the 3 treatment groups will be performed using a one-way Analysis of Covariance, including the baseline over the counter analgesic usage and treatment group in the model. Pairwise comparisons of the treatment groups will be made using a two-sample t-test. While the primary assessment will be based on Visit 12 (after 18 weeks of treatment) summaries will also be prepared for each of the other visits. If data are missing, a last observation carried forward procedure will be used, including the baseline, if necessary.

Changes in over the counter analgesic use during the active treatment stage of the study (Stage 3) will also be summarized.

13.2.2.3 Overall Analgesic Use

The change and percent change in daily average use of all analgesics (prescription and over the counter) comparing the baseline menstrual cycle (28 days) to the 28 days leading up to the last day of dosing in Cycle 1 (Week 18) will be summarized for each treatment group. For each subject, the total number of pills or tablets of analgesics taken during each 28 day menstrual cycle will be calculated, and the daily average use of prescription analgesics will be determined by dividing the total number of pills/tablets of analgesics taken during the 28 day nominal period by 28. The percent change from baseline in the analgesic usage will be determined by subtracting the baseline analgesic usage from the analgesic usage during the last nominal 28 day menstrual cycle, dividing by the baseline analgesic usage, and multiplying by 100%.

An overall comparison among the 3 treatment groups will be performed using a one-way Analysis of Covariance, including the baseline analgesic usage and treatment group in the model. Pairwise comparisons of the treatment groups will be made using a two-sample t-test. While the primary assessment will be based on Visit 12 (after 18 weeks of treatment) summaries will also be prepared for each of the other visits. If data are missing, a last observation carried forward procedure will be used, including the baseline, if necessary.

Changes in analgesic use during the active treatment stage of the study (Stage 3) will also be summarized.

13.2.2.4 BBSS Physician Reported Scores

The BBSS score incorporating the two physician-reported scores will be analyzed to compare the baseline menstrual cycle to a similar period leading up to the last day of dosing in Cycle 1 (Week 18). An overall comparison among the 3 treatment groups will be performed using a one-way Analysis of Covariance, including baseline BBSS score and treatment in the model. Pairwise comparisons of the treatment groups will be made using a t-test. While the primary assessment will be based on Visit 12 (after 18 weeks of treatment) summaries will also be prepared for each of the other visits. [REDACTED]

The BBSS patient and physician scores during the active treatment stage of the study (Stage 3) will also be summarized.

13.2.2.5 BBSS Patient Reported Scores

The percent change from baseline in each of the daily average combined BBSS patient-reported scores (dysmenorrhea, dyspareunia and non-menstrual pelvic pain) will be analyzed to compare the baseline menstrual cycle to a similar period leading up to the last day of dosing in Cycle 1 (Week 18). An overall comparison among the 3 treatment groups will be performed using a one-way Analysis of Covariance, including baseline BBSS score and treatment in the model. Pairwise comparisons of the treatment groups will be made using a two-sample t-test. While the primary assessment will be based on Visit 12 (after 18 weeks of treatment) summaries will also be prepared for each of the other visits. [REDACTED]

The BBSS patient scores during the active treatment stage of the study (stage 3) will also be summarized

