Study Endpoints	
The study endpoints will be:
 
Primary Endpoint
 
• Change and percent change in the individual BBSS scores of the three patient reported outcomes (dysmenorrhea, dyspareunia and non-menstrual pelvic pain) by study visit and treatment cycle. 
Secondary Endpoints
 
• Change in daily average use and percent change of prescription medications from the baseline menstrual cycle to the matching period leading up to Week 18, the last day of dosing of the first cycle of treatment.• Change in daily average use and percent change of over the counter medications from the baseline menstrual cycle to the matching period leading up to Week 18, the last day of dosing of the first cycle of treatment, calculated based on days with reported values.• Change in daily average use and percent change of overall medication use, prescription and over the counter, from the baseline menstrual cycle to the matching period leading up to Week 18, the last day of dosing of the first cycle of treatment, calculated based on days with reported values.• Change and percent change in BBSS score incorporating the two physician reported scores by study visit and treatment cycle.• Change from baseline in pain assessed using a Visual Analog Scale (VAS) by study visit and treatment cycle.• Change from baseline in daily average dysmenorrhea and non-menstrual pelvic pain using an 11-point numerical rating scale (NRS) by study visit and treatment cycle.
Statistical Methods:	A Statistical Analysis Plan (SAP) will be developed prior to unblinding of the data that will outline all planned analyses and

[figure not shown]
analysis populations. The first efficacy analysis will be conducted when all subjects complete the first cycle of treatment. A second analysis will summarize the subject's additional treatment cycles which will be conducted after all subjects complete study treatment and follow-up.

[figure not shown]
Summaries for quantitative variables include the sample size, mean, median, standard deviation, minimum, and maximum. Summaries for categorical variables include the number and percent of patients for each outcome. All summaries will be prepared for each treatment group.

[figure not shown]
Summaries will be prepared for each treatment group of subject accountability, baseline demographic, and medical history data.

[figure not shown]

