13.2.2.1 Prescription Analgesic Usage

The change and percent change in daily average use of prescription analgesics comparing the baseline menstrual cycle (28 days) to the 28 days leading up to the last day of dosing in Cycle 1 (Week 18) will be summarized for each treatment group. For each subject, the total number of pills or tablets of prescription analgesics during each 28 day menstrual cycle will be calculated, and the daily average use of prescription analgesics will be determined by dividing the total number of pills/tablets of prescription analgesics taken during the 28 day nominal period by 28. The percent change from baseline in the prescription analgesic usage will be determined by subtracting the baseline prescription analgesic usage from the prescription analgesic usage during the last nominal 28 day menstrual cycle, dividing by the baseline prescription analgesic usage, and multiplying by 100%.

An overall comparison among the 3 treatment groups will be performed using a one-way Analysis of Covariance, including the baseline prescription analgesic usage and treatment group in the model. Pairwise comparisons of the treatment groups will be made using a two-sample t-test. While the primary assessment will be based on Visit 12 (after 18 weeks of treatment) summaries will also be prepared for each of the other visits. If data are missing, a last observation carried forward procedure will be used, including the baseline, if necessary.

Changes in prescription analgesic use during the active treatment stage of the study (Stage 3) will also be summarized.

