5. ENDPOINTS

Efficacy endpoints will be:

- Changes in patient and physician reported BBSS scores
- Number of subjects becoming amenorrheic
- Changes in pain assessments
- Changes in analgesic use

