6. STATISTICAL METHODOLOGY AND ANALYSES

6.1 GENERAL CONSIDERATIONS

Standard statistical methods will be employed to analyze all data. It is anticipated that the following techniques may be used: paired t-test; independent two-sample t-test; ANOVA; chi-square test; and Fisher's exact test. Assumptions of normality will be tested using the Shapiro-Wilk test. If distributional assumptions are violated, non-parametric techniques, such as the Wilcoxon signed-rank test, Wilcoxon rank-sum test, and Kruskal-Wallis test, will be employed. Summaries for quantitative variables will include the sample size, mean, median, standard deviation, minimum, and maximum. Summaries for categorical variables will include the number and percent of patients for each outcome. Statistical significance will be declared if the two-sided p-value is ≤ 0.05 . Additional statistical analyses, other than those described in this SAP, may be performed if deemed appropriate.

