6.7.5 BBSS Patient Reported Scores

Patient reported daily BBSS component scores (dysmenorrhea, pelvic pain, dyspareunia) and total score and the change from baseline in each will be summarized from patient diaries.

The statistical significance of the change from baseline within treatment groups will be based on a paired t-test or Wilcoxon signed-rank test, as appropriate. The change from baseline will be compared between groups using a t-test or Wilcoxon rank-sum test, as appropriate.

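### For the primary patient BBSS scores the protocol tests percent change and the SAP tests only absolute change; separately, percent change in analgesic use has no visible rule for a zero baseline

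*Protocol*

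**What the plan says.** Protocol references are to the last version in the file, the one after Amendment 8US; the SAP says that it follows Amendment 9.

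**Patient BBSS scores (primary).** The Synopsis and Protocol 8.1 and 10.1 define the endpoint as "Change and percent change in the individual BBSS scores of the three patient reported outcomes". Protocol 13.2.2.5 then analyses "The percent change from baseline in each of the daily average combined BBSS patient-reported scores". The overall three-group test is an ANCOVA with baseline score and treatment. After it, "Pairwise comparisons of the treatment groups will be made using a two-sample t-test", with no baseline term.

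SAP 5 lists "Changes in patient and physician reported BBSS scores" and marks nothing as primary. SAP 6.7.5 says "The change from baseline will be compared between groups using a t-test or Wilcoxon rank-sum test, as appropriate". The techniques in SAP 6.1 begin "paired t-test; independent two-sample t-test; ANOVA; chi-square test" and do not include ANCOVA.

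**Analgesic use (secondary).** Protocol 13.2.2.1 computes each woman's percent change by "dividing by the baseline prescription analgesic usage, and multiplying by 100", and 13.2.2.2 by "dividing by the baseline over the counter analgesic usage, and multiplying by 100". Protocol 13.2.2.3 does the same for overall use. SAP 6.7.3 tests both change and percentage change for prescription, non-prescription and total use.

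**Who may have no baseline use.** Protocol 8.3.1 admits a woman who has been prescribed medication, or who takes over-the-counter medication at prescription strength; no minimum use is visible. Protocol 12.1.1 asks women to take analgesics only when pain requires it.

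**The concern.** Two documents that should specify one primary comparison specify different outcome variables. Percent change weights a woman with a low baseline more heavily than absolute change does. The two are different estimates and can fall on opposite sides of 0.05 in the same data. If nothing is settled before unblinding, the choice between them, and between the t-test and the rank test, can be made after the results are seen.

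The analgesic issue is one of definition. A woman who enters by the over-the-counter route may take no prescription analgesic in her baseline cycle, and a woman who enters on a prescription may take nothing over the counter. Her percent change then has a zero denominator. If she is left out, the percent-change test is run on a subset selected by baseline use, although Protocol 13.2.2 and SAP 4.1 define the analysis population as everyone randomised and treated.

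**Working it through.** **1. Does plain 'change' in SAP 6.7.5 mean absolute change?** SAP 6.7.3 names change and percentage change together for analgesics, and SAP 6.7.7 names percentage change for VAS. The SAP writes percentage when it means it, so 6.7.5 reads as absolute change. At the pairwise level the conflict is therefore percent versus absolute, plus the SAP's rank-test option. The baseline adjustment missing from the SAP belongs only to the protocol's overall test.

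**2. The plan's own figure.** Protocol 13.1 gives 80% power with 18 per group for a two-sample t-test. The assumed difference and SD are not visible, so the figure cannot be reproduced directly. Back-solving at two-sided 0.05:
- normal approximation: d = (1.960 + 0.842) × √(2/18) = 0.934
- noncentral t: d = 0.961, which gives 84% power at the planned 20 per arm.

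This d is tied to no visible endpoint and serves only as a reference value.

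**3. How often do the two metrics disagree?** Assumptions, since the documents give no SDs or correlations: baseline and follow-up lognormal with mean 1, all baselines above zero, CV 0.3 to 0.7, log-scale correlation 0.3 to 0.7, 20 per arm, 20,000 trials per setting, 12 mg versus placebo. Proportional effect: follow-up multiplied by 0.8 on placebo and by 0.8 × 0.7 on active. Additive effect: 0.20 subtracted on placebo and 0.44 on active, floored at zero.

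| Pairwise t-tests, correlation 0.5 | CV 0.3 | CV 0.5 | CV 0.7 |
|---|---|---|---|
| Disagree at 0.05, proportional effect | 17% | 26% | 21% |
| Disagree at 0.05, additive effect | 16% | 21% | 19% |

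Over all settings the range is about 7% to 32%. With no true effect, accepting whichever test rejects gives a type I error of about 6% to 8%.

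A different assumed model, a 0–3 score with follow-up means of 80% and 50% of baseline, gives 25% disagreement. There the absolute t-test rejects more often (63% versus 45%); in the lognormal model the percent t-test does. Which metric rejects more often depends on the assumptions.

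**4. Does either metric have more power once both are adjusted?** ANCOVA contrasts on both, lognormal model, CV 0.5, correlation 0.5:

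| Effect | Percent change | Absolute change |
|---|---|---|
| Proportional | about 68% | about 71% |
| Additive | about 47% | about 41% |

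Neither wins throughout.

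**5. What baseline adjustment is worth.** With equal SDs, unadjusted change has variance 2σ²(1 − r) and the ANCOVA residual has σ²(1 − r²), a ratio of (1 + r)/2. The effective effect size is 0.961/√((1 + r)/2), at 20 per arm with 38 df:

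| r | Ratio | Effective d | Power (unadjusted: 84%) |
|---|---|---|---|
| 0.3 | 0.65 | 1.192 | 95.7% |
| 0.5 | 0.75 | 1.110 | 92.8% |
| 0.7 | 0.85 | 1.043 | 89.5% |

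**6. The analgesic formula at zero.** Pills per 28 days, baseline to end:

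| Counts | Change per day | Percent change |
|---|---|---|
| 10 to 5 | −0.179 | −50% |
| 1 to 5 | +0.143 | +400% |
| 0 to 5 | +0.179 | undefined (5/0) |
| 0 to 0 | 0 | undefined (0/0) |

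The visible rules are imputation of no change for missing post-baseline data (Protocol 13.2.2) and last observation carried forward (13.2.2.1 to 13.2.2.3). Both concern missing data. A rank test does not help, because there is no value to rank. The share of zero baselines is not given. If 2, 4 or 6 of 20 per arm were left out, power of the percent-change t-test at the reference d of 0.961 would fall from 84% to 80%, 75% or 69%.

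**The case against.** - **The SAP is within the protocol.** Absolute change is half of the stated primary endpoint, and Protocol 13.2 leaves the detail of the analyses to a SAP completed before unblinding. This stands. A reader might infer that the SAP brought in a foreign measure; it did not. What remains is that it drops the metric of 13.2.2.5 without explanation while stating that it adheres to the protocol.
- **The p-values are only descriptive.** Protocol 13.3 says that they quantify differences. That lowers the stakes, but the same section and SAP 6.1 declare significance at 0.05, and the estimates differ as well as the p-values.
- **The analgesic gap touches only half of some secondary endpoints.** This stands. A reader might infer that women with zero baseline use are lost from the analgesic analysis. The documents do not say so, and SAP 6.7.3 also tests absolute change, which is defined for them. A rule for zero baselines could also sit in redacted or non-visible text (parts of Protocol 8.3.1 and 13.2.2.5, SAP 6.7.1 and 6.7.2).
- **Unadjusted pairwise tests are agreed.** Protocol and SAP both specify them, and the sample size rests on them. Moving to adjusted contrasts is an improvement, not the repair of a contradiction.
- **VAS and NRS.** It is tempting to extend the point to them, because Protocol 10.1 says change while the analyses use percentage change. But Protocol 13.2.2.7 and SAP 6.7.7 agree on percentage change for VAS, and Protocol 13.2.2.8 states it for NRS. No change is warranted there.

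**Conclusion.** The point holds in two parts and should be fixed before unblinding.

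First, the primary patient BBSS comparison is tested on percent change in the protocol and on absolute change in the SAP, with no declared departure. This rests on visible text alone. Its practical size, disagreement in about 7% to 32% of trials, rests on the assumed score model, CVs, correlations and effects.

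Second, and of less weight, individual percent change in analgesic use is undefined at a zero baseline that the entry criteria and as-needed use allow. How many women this affects is unknown. A zero in one class is foreseeable; zero total use is less likely.

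A reader might conclude that absolute change is the more powerful metric. The like-for-like comparison does not support that: percent change does better with an additive effect and slightly worse with a proportional one. The gain from 84% to between 89% and 96% comes from adjusting for baseline, and assumes d = 0.96 and equal SDs.

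**What to change.** Before Stage 2 unblinding:

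1. Name one tested metric for the patient BBSS comparison and use it in the Synopsis, Protocol 8.1, 10.1 and 13.2.2.5, and SAP 5 and 6.7.5. Absolute change is the natural choice: it is already in the endpoint, it is what the SAP tests, and it is defined when a single item such as dyspareunia scores zero at baseline.
2. Take the dose-versus-placebo comparisons as contrasts from the ANCOVA with baseline that Protocol 13.2.2.1 to 13.2.2.3 and 13.2.2.5 already specify for the overall test. Write this into SAP 6.7.3 and 6.7.5, add ANCOVA to SAP 6.1, and keep the t-test or rank test as a sensitivity check.
3. Test absolute change for prescription, over-the-counter and total analgesic use. Report percent change descriptively, per arm, as mean change divided by mean baseline, which stays defined when individual women have zero use.

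The cost is a protocol amendment and a SAP revision, with no new data. The downside is that the percent-change half of the primary endpoint becomes descriptive, with some loss of power if the effect is additive (about 47% to 41% in the setting above). If the sponsor prefers to test percent change, the documents must still be aligned and a zero-baseline rule written.

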13.2.2.6 Menstrual or Non-menstrual Vaginal Bleeding

The number of days and intensity of menstrual and non-menstrual vaginal bleeding will be summarized from the diary data. The total number of days and average intensity will be summarized from the days preceding each visit. An overall comparison among the 3 treatment groups will be performed on both the total number of days and average intensity using a one-way Analysis of Covariance, including the baseline score (number of days or average intensity) and treatment in the model. Pairwise comparisons of the treatment groups will be made using a two-sample t-test. While the primary assessment

will be based on Visit 12 (after 18 weeks of treatment) summaries will also be prepared for each of the other visits and visit post-recovery menses. If data are missing, a last observation carried forward procedure will be used, including the baseline, if necessary.

The number of days and intensity of menstrual and non-menstrual vaginal bleeding will also be summarized from active treatment (Stage 3) diary data collected.

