8.2 Study Design

8.2.1 Overview of Study Design

This study is a phase 2, 3-arm-study with an 18 week active dosing period and an option for subjects to receive 2 additional 16-week cycles of active treatment at their randomized dose (6 mg or 12 mg/day). Placebo subjects who elect additional treatment will receive treatment at 12 mg/day. The treatment dose will remain double-blind. The study will be conducted in 3 stages. In the first stage, women will undergo a baseline assessment period with no treatment. This stage will last as long as it takes to record at least one full menstrual cycle (ovulation until ovulation).

Subjects will be provided with a daily diary with which to record patient reported scores for the three elements of endometriosis pain: dysmenorrhea, non-menstrual pelvic pain and dyspareunia (BBSS).

For stage 2, following the baseline assessment period, at Visit 3, 60 subjects will be randomized into one of 3 arms in a 1-1-1 fashion. The start of dosing should commence as soon as possible after ovulation following the end of the previous menstrual event.

Once the 18 week active dosing period is completed, subjects will be followed until menses has returned (usually within 21 days or less). Subjects may elect to receive up to 2 additional cycles of treatment at their randomized dose (6 mg or 12 mg/day), placebo-treated subjects will receive treatment at 12 mg/day. In stage 3 all subjects will receive active treatment but the treatment dose will remain double-blind. For subjects who do not choose additional treatment cycles, this will be their final follow-up visit. During the follow-up period subjects will continue to record study information in the daily diary.

For stage 3, subjects who are eligible to receive additional cycles of treatment and who elect to continue treatment will be scheduled at 21 ± 2 days after start of bleeding in their first menses after Visit 12 (recovery menses). Subjects will receive 2 cycles of treatment separated by an off-drug interval (ODI), after which they will be

followed until menses has returned. During the follow-up period subjects will continue to record study information in the daily diary. The final follow-up visit will be scheduled after blood flow has stopped.

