8.3 Selection and Withdrawal of Subjects

Subjects for the study will be selected during screening based on the inclusion and exclusion criteria and clinical assessments listed below. Subjects will be discontinued from the study prematurely if:

- Unacceptable adverse events occur considered by the investigator to be associated with use of the study drug
- The subject requests to be withdrawn from the study
- Any of the following occur:
 - ALT or AST >8xULN

- ALT or AST $>5\times$ ULN for more than 2 weeks
- ALT or AST $>3\times$ ULN **and** (TBL $>2\times$ ULN **or** INR >1.5)
- ALT or AST $>3\times$ ULN with the appearance of fatigue, nausea, vomiting, right upper quadrant pain or tenderness, fever, rash and/or eosinophilia ($>5\%$)
- A need arises for concomitant medication prohibited by the protocol
- The Principal Investigator decides that it is in the subject's best interest
- The subject is noncompliant with the protocol
- Any subject who develops an endometrial thickness ≥ 18 mm will undergo endometrial biopsy. The endometrial biopsy will be forwarded to a member of the Expert Panel for expedited review. If the biopsy shows EIN or hyperplasia (per Expert Panel review), subject will be discontinued from the study. If EIN or hyperplasia is diagnosed the sponsor will be notified and subject discontinued from the study. Appropriate follow up treatment will be provided as deemed necessary by the investigator.
- Any subject who experiences heavy bleeding (bleeding intensity of 4 or more per the Daily Diary Card in [Appendix 3](#)) for 7 consecutive days or more will be discontinued from the study. This does not apply if heavy bleeding occurs in the first recovery menses after withdrawal of drug at the end of treatment, or is no heavier than bleeding was prior to treatment.
- Any subject who develops an endometrial thickness ≥ 18 mm and excessive bleeding that requires dilatation and curettage or hysterectomy will be discontinued from the study and undergo endometrial biopsy. Women with such findings will not be eligible for extension of treatment. Appropriate follow up treatment will be provided as deemed necessary by the investigator.
- Subjects with a biopsy that shows clear evidence of neoplasia, as determined by the expert panel, will be discontinued and be ineligible for extension of treatment.

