13.3 General Statistical Issues

A Statistical Analysis Plan (SAP) will be developed prior to the analyses of the first cycle of treatment. Two analyses will be conducted. The first analysis will occur when all subjects have completed the first cycle of treatment (Week 18) and the second will be conducted once all subjects have completed the active treatment stage of the study (Stage 3).

Statistical significance will be declared if the two-sided p-value is ≤ 0.05 . Since the study was not powered for efficacy assessments based on statistical hypotheses, the p-values reported at the conclusion of the study are being reported to quantify the difference in the treatment effect between treatment groups.

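### The LOCF rule for bleeding also covers the off-drug recovery-menses visit, so an on-drug zero can stand in for an unrecorded recovery bleed (minor)

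*Protocol*

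**What the plan says.** All protocol references are to the latest version in the file.

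- **Measure.** Section 13.2.2.6 takes bleeding from the diaries: "The total number of days and average intensity will be summarized from the days preceding each visit". It gives no length for that window. Visit 12 is the primary assessment.
- **Visits covered.** Beyond Visit 12, summaries are planned for "each of the other visits and visit post-recovery menses. If data are missing, a last observation carried forward procedure will be used".
- **Missing data.** In full, that last sentence reads "If data are missing, a last observation carried forward procedure will be used, including the baseline, if necessary". It names no visit to which it does not apply.
- **State at the recovery visit.** Section 8.2.1: "Once the 18 week active dosing period is completed, subjects will be followed until menses has returned (usually within 21 days or less"). Women keep the daily diary during this follow-up.
- **On-drug amenorrhea.** SAP section 5 lists "Number of subjects becoming amenorrheic" among the efficacy endpoints.
- **Recovery bleeding.** Section 8.3 discontinues women for prolonged heavy bleeding, with an exemption: "This does not apply if heavy bleeding occurs in the first recovery menses after withdrawal of drug at the end of treatment".
- **A second imputation rule.** Section 13.2.2 imputes no change from baseline for missing post-baseline data in the first-cycle efficacy analyses. Nothing says how this fits with LOCF in 13.2.2.6.
- **Timing.** Section 13.3: "The first analysis will occur when all subjects have completed the first cycle of treatment (Week 18"). Section 13.2 and SAP section 1 instead wait until all women have completed Stage 2.

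**The concern.** LOCF assumes that the last recorded value is a fair substitute for the missing one. That assumption fails when the two values come from different states. Every value up to Visit 12 in Stage 2 is recorded on treatment. The recovery visit is recorded after withdrawal and is timed by the return of menses. For a woman who stopped bleeding on drug, the carried value is zero, while the quantity being summarized is a bleed.

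The recovery summary shows what bleeding looks like once drug is stopped. Zeros carried from the on-drug period would pull it down in any arm where amenorrhea occurs. LOCF also merges two situations that differ after withdrawal: recovery data not recorded, and menses not yet returned.

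In the original protocol version the same LOCF sentence followed summaries of interim visits only. The recovery visit was added later, so its coverage by LOCF may be a side effect of drafting. That history is background and is not itself an error.

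**Working it through.** The documents give no bleeding figure to reproduce: no expected number of bleeding days, no amenorrhea rate and no missingness rate. The planned arm size is 20 (section 13.1). Everything else below is an assumption, used only to show how the rule behaves.

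**Formula.** For one arm, let R be the true mean recovery bleed, L the mean value carried forward, and m the share of women without recovery data. Assume that the women with missing data have the same true mean R.

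- Mean under LOCF = (1 - m)R + mL
- Bias = (1 - m)R + mL - R = -m(R - L)
- Relative bias = -m(1 - L/R)

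With L = 0 the relative bias is -m, whatever the value of R. With L = R it is zero. If L exceeds R the sign reverses. The same algebra applies to mean intensity.

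**Numbers, with R = 7 days assumed.** Three cases for the carried value: all zero (L = 0); half zero and half a baseline-like 5 days (L = 2.5); all 5 days (L = 5).

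| Missing of 20 | m | L = 0 | L = 2.5 | L = 5 |
|---|---|---|---|---|
| 1 | 0.05 | 6.65 (-5.0%) | 6.775 (-3.2%) | 6.90 (-1.4%) |
| 2 | 0.10 | 6.30 (-10.0%) | 6.55 (-6.4%) | 6.80 (-2.9%) |
| 4 | 0.20 | 5.60 (-20.0%) | 6.10 (-12.9%) | 6.60 (-5.7%) |

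Worked example, 2 missing and L = 0: 0.90 x 7 + 0.10 x 0 = 6.30, and 6.30/7 - 1 = -10%. If R is also 5, the last column shows no bias at any m.

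**Which value is carried.** Under 13.2.2.6 as worded, it is the last diary-based value, so zero for a woman amenorrheic at Visit 12. Under the no-change rule in 13.2.2, it is her baseline value, which covers a menstrual cycle. The first reading gives the L = 0 column and the second something close to the L = 5 column. The text does not choose between them.

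**How data come to be missing.** The rule acts only where the diary itself has no recovery data. Under the trigger in 13.2 and SAP section 1, the analysis follows completion of Stage 2. The synopsis and SAP section 3.1 describe Stage 2 as including follow-up until menses returns. Missing data would then come from loss to follow-up, early withdrawal or unreturned diaries, at a rate not given.

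**The case against.** The case against giving this much weight is strong, and most of it stands.

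- **Missingness by design.** A reader might infer from the Week 18 wording in 13.3 that the first analysis is cut before the last women bleed, so that recovery data are missing by design. The documents do not support that. Section 13.2 and SAP section 1 both set the trigger at Stage 2 completion, and that stage runs until menses returns. What remains is an inconsistent phrase in 13.3.
- **Visit versus diary.** A missed visit is not missing bleeding data, because the diary continues through follow-up. A woman whose diary shows that menses has not returned has an observed zero, and no imputation arises.
- **Distortion between arms.** A reader might infer that placebo women carry forward normal cycling values, so that the comparison tilts toward active drug. The window before each visit has no stated length. If it is short, a placebo woman between periods could also carry a zero. The distortion is possible but not shown.
- **Rebound.** Section 8.3 says only that heavy bleeding in the first recovery menses, if it occurs, does not trigger discontinuation. It does not say that the recovery bleed exceeds baseline.
- **Importance.** Visit 12 is the primary bleeding assessment. For the recovery visit 13.2.2.6 promises only summaries. Bleeding days and intensity are not in the visible endpoint lists of the current protocol, and the amenorrhea count in SAP section 5 is not affected by this mechanism.
- **The SAP.** The visible SAP contains no LOCF rule, and sections 6.7.1 and 6.7.2 cannot be seen. They may already handle this visit differently.

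None of this makes an on-drug value a sound substitute for an off-drug one. The sentence in 13.2.2.6 still allows that substitution.

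**Conclusion.** The point holds in a limited, minor form. As worded, 13.2.2.6 permits an on-drug value, zero for an amenorrheic woman, to be entered as her recovery bleed. The direction is certain whenever the carried value is below the true bleed. The relative shortfall is at most the missing share (for carried values between zero and the true bleed), and it is reached only if every carried value is zero. It shrinks or vanishes if baseline values are imputed. The percentages above rest on assumed bleeding days and assumed missing counts, so the actual size cannot be stated. The consequence is confined to a supporting descriptive summary. No conclusion about Visit 12, or about one arm against another, follows from it.

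**What to change.** 1. In 13.2.2.6, limit LOCF to visits up to and including Visit 12.
2. Summarize the post-recovery-menses visit from observed diary data, by arm. Alongside, give the number of women with no recovery data and, separately, the number whose menses had not returned.
3. State whether the no-change rule in 13.2.2 or the LOCF rule in 13.2.2.6 governs missing bleeding data.
4. Align the Week 18 wording in 13.3 with the Stage 2 completion trigger in 13.2 and SAP section 1.
5. Check that the SAP's bleeding section, not visible here, says the same.

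The cost is a few sentences and one or two table rows. The recovery summary will include fewer women, and it is unbiased only if the missingness is unrelated to recovery bleeding, which the added counts help a reader to judge. If Stage 2 completion is already the working trigger, the data cut does not move.
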